Statistical Methodology	Proportion of patients completing the study will be calculated and the trial will be deemed successful if the number of patients completing the protocol exceeds the futility threshold of 60%. Progression-free survival, the secondary endpoint, will be estimated by the Kaplan-Meier method and compared with historic controls using the log-rank test.

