1.3 Immune Checkpoint Inhibitor Therapy

Immune checkpoint inhibitor (ICI) therapy has assumed increasing importance in the management of bladder cancer. ICI agents function to nonspecifically stimulate the patient's immune response and decrease tumor immune evasion by inhibiting negative regulators of the immune response. In bladder cancer, most interest has attached to monoclonal antibodies which block the immunosuppressive surface receptor PD-1 or its ligand PD-L1²⁵.

Three PD-1 or PD-L1 inhibitors (avelumab, nivolumab, and pembrolizumab) are FDA-approved for second-line use in platinum-refractory advanced bladder cancer, based on clinical trials which showed objective response rates of 15-20%²⁶⁻³⁰. Two agents (atezolizumab and pembrolizumab) are FDA-approved for first-line use in patients who are ineligible for platinum-based chemotherapy, based on clinical trials showing objective response rates of 25-30% in this setting^{31,32}. Finally, avelumab has recently gained FDA approval for use as maintenance therapy following initial response to chemotherapy in advanced/metastatic bladder cancer, with clinical trials demonstrating an improvement in median overall survival from 14 to 21 months³³.

More recent efforts have explored a role for ICI treatments in the neoadjuvant setting. Two clinical trials, ABACUS and PURE-01, explored the use of neoadjuvant atezolizumab and pembrolizumab respectively, and reported pathologic complete response (pCR, meaning ypT0 N0) rates of 31% and 37%, respectively^{34,35}. While several other ongoing trials exist in this space, only a single trial has enrolled significant numbers of patients with clinical node-positive disease. In this trial, NABUCCO, patients with cN+ disease represented 42% of total enrollment. Neoadjuvant treatment with dual ICI agents (the PD-1 inhibitor nivolumab and the CTLA-4 blocker ipilimumab) resulted in an overall pCR rate of 46%³⁶.

Given their widespread clinical use in bladder and other malignancies, the adverse effect profile of ICI agents is well characterized. In the second-line trials cited above, for example, grade ≥ 3 adverse events occurred in 5-18% of patients and most notably

included autoimmune reactions at various sites including pneumonitis, colitis, and hepatitis²⁶⁻³⁰.

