2.3 Primary Endpoints

2.3.1 The primary endpoint of the study is feasibility of RC after ICI + PULSAR, defined as the proportion of enrolled patients who complete three courses of PULSAR followed by radical cystectomy while remaining on ICI therapy, within sixteen weeks of initiation of PULSAR. It is anticipated that reasons for protocol non-completion may include progression to nonresectable disease and patient intolerance of treatment.

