9.0 STATISTICAL CONSIDERATIONS

9.1 Study Design/Study Endpoints

This is a single institution, single arm, phase II trial. We hypothesize that the combination of standard-of-care ICI with PULSAR will be feasible and does not result in delays in treatment. We define a target rate of protocol completion (completion of radical cystectomy within sixteen weeks of initiation of PULSAR) of 90%, with a lower boundary of futility at 60%.

The secondary endpoint is efficacy, defined by 2-year recurrence-free survival.

As discussed above, we additionally plan to assess safety (defined by the 90-day rate of Clavien-Dindo Grade \geq III complications following radical cystectomy); pathologic outcomes; rates of residual disease at surgery; and ureteroenteric anastomotic stricture rate.

If the incidence of Grade 3 or higher treatment-related adverse events convincingly exceeds 50%, a threshold we are comfortable with given the potential benefit of the regimen as well as our experience in managing the side effects in this patient population, we will temporarily halt the study and carefully review the available data at that point in order to suggest a potential modification. If we determine that high rates of adverse events are intrinsically related to protocol and no modification will reasonably decrease this rate to an acceptable threshold (below 50%), then we will terminate the study.

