9.2 Sample Size and Accrual

For the primary endpoint of feasibility, we define a target rate of protocol completion (completion of radical cystectomy within sixteen weeks of initiation of PULSAR) of 90%, with a lower boundary of futility at 60%. A sample size of 24 patients provides 91% power to reject a 60% completion rate at a two-sided alpha of 0.05. Of note, this sample size was employed in the recent NABUCCO trial, which addressed a similar high-risk patient cohort³⁶. Allowing a 10% drop out rate increases the desired enrollment to a total of **27 patients**. Given the desired enrollment of 27 patients and the three-year trial period, this will require accrual of nine patients per year across all sites.

For the secondary endpoint of progression-free survival, the trial-eligible subset of our recently published historic series of cN+ bladder cancer patients achieved a 2-year recurrence-free survival rate of 30%¹⁵. A sample size of 24 patients provides 90% power to detect a 27% absolute increase in 2-year recurrence free survival with a one-sided alpha of 0.10 using the Kaplan-Meier log-rank test.

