9.3 Data Analyses

The primary endpoint, protocol completion, will be assessed by calculating the proportion of patients completing radical cystectomy within sixteen weeks of initiating PULSAR treatment. If the proportion of patients undergoing cystectomy exceeds 60%, the null hypothesis (that use of ICI+PULSAR+RC is not feasible) will be deemed to have been rejected.

For the secondary endpoint, progression-free survival will be determined as described above, and will be reported by means of Kaplan-Meier survival curves, median progression-free survival time, and proportion of patients without progression at two years. Comparison will be made to the trial-eligible subset of patients in a historic control series using the log-rank test. The 2-year progression-free survival rate in the historic cohort was 30%. The null hypothesis will be rejected if the one-sided *p* value for the comparison is less than 0.10.

Additional planned analyses include the following, all of which will be reported with simple descriptive statistics (*n* / *N* and percentage):

Major complication rate: A major surgical complication will be defined as any postoperative complication of Clavien-Dindo Grade III or higher.

Pathologic outcomes: Pathologic outcomes will be defined as follows, based on the final surgical pathology report:

1. Pathologic complete response: no viable disease remaining in the specimen (ypT0 N0).
2. Pathologic non-muscle-invasive downstaging: primary tumor without muscle invasion, and no viable disease in lymph nodes (\leq ypT1 N0).
3. Pathologic organ-confined downstaging: primary tumor confined to detrusor muscle, and no viable disease in lymph nodes (\leq ypT2 N0).
4. Nodal complete response: no viable disease in lymph nodes, regardless of primary tumor stage (ypTany N0).

Residual disease: Residual disease at surgery will be defined as follows:

1. Microscopic residual disease (R1) will be defined as any positive soft tissue margin on the final surgical pathology report, excluding carcinoma *in situ* at ureteral margins.
2. Gross residual disease (R2) will be defined as any grossly positive tissue margin reported on a pathology report, *or* the operating surgeon's subjective report of grossly unresectable disease including bulky matted lymph nodes.

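### The analysis in 9.1 to 9.3 counts cystectomy by week 16 only, while the primary endpoint in 2.3.1 also requires three PULSAR courses and staying on ICI

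*Combined protocol and SAP*

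**What the plan says.** Section 2.3.1 gives the formal definition of the primary endpoint: "the proportion of enrolled patients who complete three courses of PULSAR followed by radical cystectomy while remaining on ICI therapy", inside a sixteen-week window that opens when PULSAR starts. It adds that "reasons for protocol non-completion may include progression to nonresectable disease and patient intolerance of treatment".

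The statistical section uses a shorter event in three places:

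- Section 9.1: "We define a target rate of protocol completion (completion of radical cystectomy within sixteen weeks of initiation of PULSAR) of 90" percent.
- Section 9.2, which sets the sample size: "we define a target rate of protocol completion (completion of radical cystectomy within sixteen weeks of initiation of PULSAR) of 90" percent.
- Section 9.3, which states the calculation: "calculating the proportion of patients completing radical cystectomy within sixteen weeks of initiating PULSAR treatment". The decision sentence then begins "If the proportion of patients undergoing cystectomy exceeds 60" percent.

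The Statistical Methodology row of the Study Summary says only that "the trial will be deemed successful if the number of patients completing the protocol exceeds the futility threshold of 60" percent, without listing what completing the protocol involves.

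Two other sections bear on the point. Section 4.8 says subjects should receive at least two ICI doses alongside PULSAR before surgery and allows a change of agent. Section 4.10 lets PULSAR end early, for example for unacceptable adverse events or intercurrent illness.

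**The concern.** Feasibility of surgery after ICI plus PULSAR is the trial's only primary objective. The endpoint in 2.3.1 fits that objective because it requires each part of the regimen to be delivered. The calculation in 9.3 requires only the last part, on time. An analyst who followed 9.3 to the letter would not compute 2.3.1.

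The two differ for one kind of patient: someone who stops PULSAR after one or two fractions, or stops ICI, and still has cystectomy by week 16. That patient is a failure under 2.3.1 and a success under 9.3. Section 2.3.1 itself expects some intolerance, so such patients are plausible. Counting them as completions would report the combined regimen as feasible in people who did not receive all of it. With two wordings in force, the choice between them could also be made after the data are seen.

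**Working it through.** **Inputs from the plan.** Analysed sample n = 24, futility rate 60%, target 90%, two-sided alpha 0.05, power 91%, dropout 10% (all 9.2). Decision rule: observed proportion above 60% (9.3).

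**1. Reproduce the plan's figures.** Exact binomial, upper tail no more than 0.025 under a true rate of 0.60. The smallest qualifying cut-off is 20 of 24:

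- P(X ≥ 20 | n = 24, p = 0.60) = 0.0134.
- P(X ≥ 20 | n = 24, p = 0.90) = 0.915, which matches the stated 91%.
- 24 / (1 − 0.10) = 26.7, so 27, as stated.

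The arithmetic in 9.2 is sound. The question is which event the 90% describes.

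**2. Compare the definitions.**

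| Component | 2.3.1 | 9.1, 9.2, 9.3 |
|---|---|---|
| Three PULSAR courses | required | not mentioned |
| Radical cystectomy | required | required |
| Still on ICI | required | not mentioned |
| Sixteen weeks from PULSAR start | required | required |

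Every 2.3.1 success is also a 9.3 success. On a common denominator, the 9.3 rate therefore equals or exceeds the 2.3.1 rate.

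**3. Size per patient.** 1/24 = 4.2 points; at full enrolment 1/27 = 3.7 points. Suppose 22 of 24 have cystectomy on time, which is 91.7% under 9.3. If one of the 22 stopped PULSAR or ICI early, 2.3.1 gives 21/24 = 87.5%. If four did, it gives 18/24 = 75.0%.

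**4. Effect on the written rule.** 0.60 × 24 = 14.4, so a pass needs at least 15 of 24. Let the true rate of cystectomy by week 16 be 0.90, and let d be the share of those patients who stopped PULSAR or ICI early. The composite rate is 0.90 × (1 − d). The documents give no value for d, so these are assumptions. The largest borrows the top of the range in 1.3, where grade 3 or higher "adverse events occurred in 5-18% of patients" in second-line ICI trials.

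| Assumed d | Expected discordant patients (24 × 0.90 × d) | Composite rate | P(X ≥ 15) | Opposite verdicts |
|---|---|---|---|---|
| 0 | 0 | 90% | 0.99995 | 0 |
| 0.05 | 1.1 | 85.5% | 0.99886 | 0.1% |
| 0.18 | 3.9 | 73.8% | 0.92763 | 7.2% |

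Because the two success sets are nested, the last column is 0.99995 minus the pass probability.

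**5. Effect on the stated power.** If 90% is the composite rate, 24 patients and 91% power stand. If 90% describes cystectomy timing only, the composite rate cannot be higher than 90%. Exact power with 20 or more of 24 is then:

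- at a composite rate of 85.5%: 0.738
- at a composite rate of 73.8%: 0.207

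**The case against.** The strongest reply is that section 9 restates 2.3.1 incompletely and does not set up a rival endpoint. Section 2.3.1 sits under the endpoint heading and is worded as the definition. Section 9.3 opens by naming the primary endpoint, and its null hypothesis refers to ICI+PULSAR+RC. Section 2.2.1 describes the full protocol as all three treatments. This much stands: 2.3.1 can be identified as the formal definition, and a reader should not infer that the plan leaves the endpoint undefined. It does not rescue section 9. Sections 9.1 and 9.2 spell out protocol completion as timely cystectomy, and 9.3 states the calculation in the same terms.

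Four stronger readings are tempting, and the documents do not support them.

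- *The decision sentence in 9.3 drops the time limit.* It directly follows the sentence that sets the sixteen-week proportion and reads naturally as referring back to it.
- *Fractions held under 4.1.3 will create many discordant patients.* That provision applies only when there is no targetable disease, and it does not say whether held means delayed or omitted.
- *ICI status will not be recorded.* The table in 5.4 has no row for it, but ICI is standard of care and the case report forms are not among the documents, so a gap in data capture cannot be shown.
- *The verdict would often flip.* The 7.2% figure needs 18% of patients with timely surgery to have stopped early. That 18% is an adverse-event rate, not a discontinuation rate. In addition, progression to nonresectable disease, and intolerance severe enough to prevent surgery, fail both definitions.

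**Conclusion.** The inconsistency is real and should be corrected. The analysis in section 9 does not measure the endpoint in 2.3.1, and any error is in the favourable direction.

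The main effect is on the reported completion rate, at 4.2 points per discordant patient with 24 analysed. The go or no-go decision is little affected: with true on-time cystectomy at 90% and an assumed 5% early-stop share, the two definitions disagree under the written rule in about 0.1% of trials. The 18% case is an extreme, not an estimate.

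The effect on power depends on what the 90% target means. The stated 91% holds for the composite only if 90% is the composite target, and 9.2 currently attaches it to cystectomy timing.

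These figures assume independent patients, a common denominator for both definitions, and the assumed early-stop shares. Step 4 uses the more-than-60% rule as written, and step 5 uses the 20-of-24 cut-off that reproduces the plan's power. The difference between those two cut-offs is a separate matter.

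**What to change.** 1. In 9.1, 9.2 and 9.3, in both the calculation and the decision sentence, replace the cystectomy-only event with the 2.3.1 composite. Possible text for 9.3: the proportion of enrolled patients who meet the Section 2.3.1 endpoint, meaning three PULSAR fractions and then cystectomy, still on ICI, by week 16 from the first fraction; the null is rejected if this proportion is above 60%. Cite 2.3.1 in the Study Summary as well.
2. State what staying on ICI requires. One option is the two-dose minimum in 4.8 with no permanent stop before surgery, a change of agent being allowed. The threshold is for the investigators to choose.
3. State in 9.2 that the 90% target applies to the composite. This keeps 24 analysed, 27 enrolled and 91% power. If the investigators believe 90% only for cystectomy timing, they should restate the target and power for the composite and reconsider the sample size.
4. Report cystectomy by week 16 as a secondary figure, with the number of patients who differ and the reason.

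The cost is a short amendment, plus a form item for ICI dose and stop dates if none exists. PULSAR dates are already recorded under 4.1.3, and no visits change. The downside is that the reported completion rate may be lower than under the looser count.

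### The primary success rule (observed completion above 60%) is not the two-sided 0.05 test that sized the trial, and passes a true 60% rate 46–49% of the time

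*Combined protocol and SAP*

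**What the plan says.** Section 9.2 gives the design values for the primary endpoint: a target completion rate "of 90%, with a lower boundary of futility at 60" per cent. The sizing statement follows: "A sample size of 24 patients provides 91% power to reject a 60% completion rate at a two-sided alpha of 0.05". A 10% allowance for drop-out raises enrolment from 24 to 27.

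Section 9.3 gives the decision rule: "If the proportion of patients undergoing cystectomy exceeds 60%, the null hypothesis (that use of ICI+PULSAR+RC is not feasible) will be deemed" rejected. The Statistical Methodology entry of the Study Summary says the same in other words: "the trial will be deemed successful if the number of patients completing the protocol exceeds the futility threshold of 60" per cent.

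No section gives a p-value, confidence limit or critical count for the primary endpoint. For the secondary endpoint, section 9.3 does give a criterion: a one-sided p-value below 0.10.

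**The concern.** Sections 9.2 and 9.3 describe two different tests of the same hypothesis. To reject 60% at two-sided alpha 0.05, the observed proportion must lie far enough above 60% that chance is an unlikely explanation. Section 9.3 asks only that it lie above 60%. When the true rate is 60%, the observed proportion falls above that value about half the time.

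This rule alone produces the trial's primary conclusion. Applied as written, it would let a regimen sitting at the sponsor's own futility boundary be reported as feasible about as often as a coin toss. The report could also attach an alpha and a power that belong to another rule.

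**Working it through.** **Inputs**
- Null rate 0.60, target rate 0.90, 24 patients, two-sided alpha 0.05, stated power 91%: section 9.2.
- Enrolment of 27: section 9.2 (24 / 0.9 = 26.7, rounded up to 27, which reproduces).
- Decision rule, observed proportion above 60%: section 9.3 and the Study Summary.

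**Formula.** With X completers among n patients and true rate p, P(X ≥ r | n, p) = Σ C(n,k) p^k (1−p)^(n−k), summed over k = r to n.

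**Step 1: reproduce the stated 91%.** A two-sided 0.05 test leaves 0.025 in the upper tail. The critical count is the smallest r with P(X ≥ r | 24, 0.60) ≤ 0.025.
- r = 19: 0.0400, too large.
- r = 20: 0.0134, acceptable.

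Power at 90% is P(X ≥ 20 | 24, 0.90) = 0.915, which matches the plan. A normal approximation with continuity correction also gives 91%. The null standard error is √(0.24/24) = 0.100 and the alternative standard error is √(0.09/24) = 0.0612, so power = Φ((0.30 − 1.96 × 0.100 − 1/48) / 0.0612) = 0.913. That version also needs 20 of 24. The sizing statement is therefore sound, and it implies a success threshold of 20/24 = 83.3%.

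**Step 2: evaluate the section 9.3 rule.** The smallest count above 60% is 15 of 24 (62.5%) or 17 of 27 (63.0%). Neither sample size can give exactly 60%, so reading the rule as 60% or more changes nothing.

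| True rate | P(success), n = 24, r = 15 | P(success), n = 27, r = 17 |
|---|---|---|
| 60% | 0.489 | 0.458 |
| 55% | 0.299 | 0.263 |
| 50% | 0.154 | 0.124 |

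At a true rate of 90% this rule succeeds more than 99.9% of the time, so the stated 91% cannot be its power. At 15 of 24 the exact 95% confidence interval is 40.6% to 81.2%.

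**Step 3: the rule that matches section 9.2.**

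| Patients analysed | Completers needed | Upper-tail error at 60% | Power at 90% | Exact 95% lower limit | Lower limit with one fewer completer |
|---|---|---|---|---|---|
| 24 | 20 | 0.0134 | 0.915 | 62.6% | 57.8% |
| 27 | 22 | 0.0155 | 0.953 | 61.9% | 57.7% |

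The two rules disagree at 15 to 19 of 24, and at 17 to 21 of 27. At a true rate of 60% with 24 patients, the probability of landing in that band is 0.489 − 0.013 = 0.476.

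**The case against.** The best defence is that section 9.3 is shorthand. Section 9.2 has already fixed the alpha, and section 9.3 speaks of rejecting a null hypothesis, so the formal test may be implied. On that reading the fault is an unstated criterion and not a commitment to a 49% error rate. This does not fit the text well. Section 9.3 makes exceeding 60% the condition for rejection, the Study Summary repeats that condition as the definition of success, and the secondary endpoint in the same section gets an explicit p-value rule.

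A second defence is that a point-estimate threshold can be a deliberate go/no-go choice in a small feasibility study. That is legitimate in principle, but such a study would not also claim an alpha, a power and a rejected null hypothesis for the same endpoint. This plan claims all three.

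Two qualifications do stand. First, not every declaration of feasibility would be weak. If the true rate is 90%, about 91.5% of trials reach 20 of 24 and only about 8.5% fall in the disputed band; the rule misleads when the true rate is near or below 60%. Second, the 46–49% range applies to the planned sizes of 27 and 24. With 25 or 26 patients analysed, the error at 60% is 42.5% or 52.1%, which leaves the conclusion unchanged.

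**Conclusion.** The concern holds. The decision rule in section 9.3 and the Study Summary does not implement the test in section 9.2. At the futility boundary its false-positive rate is 0.489 with 24 patients and 0.458 with 27, against the 0.025 upper-tail error implied by a two-sided alpha of 0.05. The sample size and the stated 91% power are correct, but they belong to a threshold of 20 of 24 and not 15 of 24.

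The calculation assumes independent patients with a common completion probability and takes the section 9.3 rule literally. Because the rule settles the primary conclusion, it must be corrected before results are known.

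**What to change.** Replace the rule in section 9.3 and the Study Summary with wording such as: *The null hypothesis of a completion rate of 60% or less is rejected if the lower limit of the exact (Clopper–Pearson) two-sided 95% confidence interval exceeds 60%. This corresponds to at least 20 completers among 24 patients, or at least 22 among 27. The exact interval will be reported.*

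The confidence-limit criterion should govern and the counts should illustrate it, because it works for any number analysed (with 25 or 26 patients the count is 21). The same amendment should name the denominator. Section 2.3.1 uses enrolled patients, section 9.2 sizes on 24 after drop-out, and section 4.13 replaces patients removed before receiving any fraction. It should also define a completer as section 2.3.1 does; the decision sentence in section 9.3 mentions cystectomy alone.

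No extra patients are needed: 24 already give 91.5% power under this rule. The change alters the primary decision criterion, so it needs a written amendment and IRB approval under section 10.6. The bar for success rises from 62.5% to 83.3% with 24 patients, or from 63.0% to 81.5% with 27, which is the standard section 9.2 already implies. If the sponsor did intend a simple go/no-go threshold at 60%, the alpha, power and null-hypothesis language for this endpoint would have to be withdrawn and the error rates above disclosed.

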1.0 BACKGROUND AND RATIONALE

1.1 Disease Background

Muscle invasive bladder cancer (MIBC) has high metastatic potential and warrants aggressive treatment. Standard-of-care treatment in MIBC involves platinum-based neoadjuvant chemotherapy (NACT) followed by radical cystectomy (RC) with pelvic lymph node dissection (PLND) and urinary diversion¹⁻³. Bladder-conserving chemoradiation therapy is an appropriate alternative in select patients, though it is used in only a minority of cases in the United States⁴. Bladder cancer carries significant morbidity and mortality and has been cited as the most expensive malignancy to manage, on a per-patient basis, in the United States^{5,6}.

Metastatic spread to regional lymph nodes is an adverse prognostic factor in bladder cancer. In several large case series reported without use of neoadjuvant chemotherapy, patients with pathologically positive lymph nodes (pN+) at radical cystectomy had 5-year overall or disease-specific survival rates of only 22-30%⁷⁻¹⁰. The addition of neoadjuvant chemotherapy (NACT) or downstaging chemotherapy (DCT) in patients with clinically positive lymph nodes (cN+) improves outcomes, particularly in those who achieve a pathologic complete response to DCT^{11,12}. However, patients who fail to respond to downstaging or neoadjuvant chemotherapy have an especially poor prognosis, with a 5-year overall survival rate of only 16% in one recent series¹³. It should also be noted that a significant proportion (up to 25-50%) of patients with bladder cancer are ineligible for chemotherapy due to medical comorbidities¹⁴.

We recently reviewed the outcomes of patients undergoing radical cystectomy at UT Southwestern with bulky cN+ bladder cancer¹⁵. Among the subset of patients who did not receive or failed to respond to DCT, the 2-year progression-free survival was only 30%, despite aggressive salvage treatment. Importantly, a majority of patients (84%) in the study received downstaging chemotherapy and all were medically eligible for chemotherapy. This suggests that chemo-ineligible patients presenting with cN+ disease were not offered curative treatment. Direct comparisons with historic literature are difficult, due to widely varying definitions of cN+ disease; however, the progression-free survival of our bulky cN+ cohort closely parallels that of the cN2-3 and cM1a cohorts within one large published series¹¹, confirming that our bulky cN+ cohort represents an especially high-risk population.

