3.1 Inclusion Criteria

- 3.1.1 Bladder cancer, confirmed pathologically on transurethral resection of bladder tumor (TURBT) or on bladder biopsy. Pure urothelial, variant urothelial, or any proportion of squamous cell carcinoma are permitted. Questions about eligibility may be resolved by consultation with UTSW pathology but formal pathologic review is not required.
- 3.1.2 Bulky, clinically node positive disease (cN+) defined as: 1) a single pelvic lymph node of ≥ 1.5 cm largest diameter on CT or MRI; or 2) multiple pelvic lymph nodes ≥ 1 cm largest diameter on CT or MRI. Pathologic confirmation is not required. Imaging to establish eligibility must have been obtained no more than 60 days prior to trial enrollment. The scans must be personally reviewed by the enrolling clinician. For imaging studies obtained outside of UT Southwestern, imaging review of node status and sign off by the enrolling investigator is required. Review and sign off by a UTSW radiologist is optional in ambiguous or questionable cases, but is not mandatory.
- 3.1.3 Age ≥ 18 years.
- 3.1.4 ECOG performance status 0-1.
- 3.1.5 Appropriate candidate for radical cystectomy, as determined by the treating urologist.
- 3.1.6 Appropriate candidate for stereotactic ablative radiotherapy, as determined by the treating radiation oncologist.
- 3.1.7 Patient is planned to initiate or is within 1-3 weeks of initiation of FDA-approved immune checkpoint inhibitor therapy based on ineligibility to receive platinum-based downstaging chemotherapy (DCT) (Cohort 1, as detailed below) or failure to achieve clinical complete response to platinum-based DCT (Cohort 2, as detailed below).

Cohort 1 (chemotherapy-ineligible) – either of:

- patient staged with bulky cN+ disease as defined above, medically ineligible to receive any platinum-based chemotherapy or, after appropriate and documented counseling, refusing to receive any-platinum-based chemotherapy; *or*
- patient staged with bulky cN+ disease as defined above, medically ineligible to receive cisplatin-based chemotherapy, with PD-L1 positive tumor (according to methodology described in the FDA approval label for the respective ICI agent)

Cohort 2 (chemotherapy non-responding) – any of:

- patient, initially staged with bulky cN+ disease as defined above, with radiologic progression after two cycles of platinum-based DCT (per RECIST 1.1 criteria: $\geq 20\%$ increase in summed short-axis diameter of visible lesions with ≥ 5 mm absolute increase)

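### The 30% PFS benchmark comes from chemotherapy-eligible patients, so it has no counterpart to Cohort 1 patients medically unfit for any platinum, yet all enrolled patients are tested against it

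*Combined protocol and SAP*

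**What the plan says.** The benchmark is introduced in section 1.1, which reviews a local series: "We recently reviewed the outcomes of patients undergoing radical cystectomy at UT Southwestern with bulky cN+ bladder cancer". The figure itself comes from one part of that series: "Among the subset of patients who did not receive or failed to respond to DCT, the 2-year progression-free survival was only 30" (per cent). The section continues: "Importantly, a majority of patients (84%) in the study received downstaging chemotherapy and all were medically eligible for chemotherapy". It then infers: "This suggests that chemo-ineligible patients presenting with cN+ disease were not offered curative treatment". Section 1.4 repeats that inference.

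The trial population is wider. Under section 3.1.7, Cohort 1 has three routes of entry:
- patients "medically ineligible to receive any platinum-based chemotherapy";
- patients who refuse platinum after counselling;
- cisplatin-ineligible patients with a PD-L1-positive tumour.

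Cohort 2 holds patients who did not respond adequately to platinum-based downstaging chemotherapy.

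Section 2.2.1 sets the PFS objective for all enrolled patients and for those who complete the full protocol. Section 9.2 says that "the trial-eligible subset of our recently published historic series of cN+ bladder cancer patients achieved a 2-year recurrence-free survival rate of 30" (per cent) and bases a 90% power statement on it. Section 9.3 plans the test: "Comparison will be made to the trial-eligible subset of patients in a historic control series using the log-rank test". The null hypothesis is rejected if one-sided p is below 0.10. Section 9 contains no PFS result by cohort, no stratification or adjustment, and no separate benchmark for Cohort 1.

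**The concern.** Calling the benchmark a trial-eligible subset invites the reader to think that the series spans the trial's eligibility range. By the protocol's own account, one group that the trial sets out to serve is absent from it. Patients unfit for any platinum may do better than the benchmark, because they can be untreated rather than chemotherapy-resistant. They may also do worse, because of comorbidity. Either way, the pooled result depends partly on how many of them are accrued.

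A rejection, or a failure to reject, could then reflect case mix rather than the added radiotherapy. Section 1.4 presents platinum-ineligible patients as part of the trial's focus, so readers will apply the PFS conclusion to them although the comparison cannot support it.

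**Working it through.** **1. Who is behind the 30%, and who is in the trial.**

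| Trial group (3.1.7) | Counterpart in the historic subset (1.1)? |
|---|---|
| Cohort 1, medically unfit for any platinum | None: all historic patients were medically eligible for chemotherapy |
| Cohort 1, cisplatin-ineligible, PD-L1 positive | Not stated. Section 1.1 says chemotherapy, not cisplatin; section 3.1.8 permits gemcitabine/carboplatin; the Appendix A checklist describes this group as carboplatin-eligible |
| Cohort 1, platinum refusers | Possible: eligible patients who did not receive downstaging chemotherapy |
| Cohort 2 | Possible: patients who failed to respond, although the series' definition of failure is not given |

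The first row takes chemotherapy in section 1.1 to mean platinum-based downstaging chemotherapy, which is how the protocol uses it.

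**2. Reproduce the plan's figure.** Inputs from section 9.2: n = 24, 2-year rate 30%, absolute gain 27 points (so 57%), one-sided alpha 0.10, power 90%. For an exact one-sample binomial test, take the smallest r with P(X ≥ r | 24, 0.30) ≤ 0.10:
- r = 10 gives 0.153, which is too large;
- r = 11 gives 0.074;
- power is P(X ≥ 11 | 24, 0.57) = 0.904.

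The stated 90% is reproduced as a comparison with a fixed 30%. A two-sample log-rank calculation would need the size of the historic subset, which is not given. Power would be 0.72 with 20 controls and 0.92 with 100.

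**3. Illustrate the sensitivity.** Let m be the share medically unfit for any platinum and q their 2-year PFS under current care. The documents give neither, so both are assumed. The true pooled no-effect rate is

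p = (1 − m) × 0.30 + m × q.

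For m = 0.50:
- q = 0.20 gives 0.15 + 0.10 = 0.25;
- q = 0.40 gives 0.15 + 0.20 = 0.35.

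For m = 0.25:
- q = 0.20 gives 0.225 + 0.05 = 0.275;
- q = 0.40 gives 0.225 + 0.10 = 0.325.

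Keep the rule at 11 or more of 24. The false-positive rate is P(X ≥ 11 | 24, p), and power for a true 27-point gain is P(X ≥ 11 | 24, p + 0.27).

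| True pooled no-effect rate | False-positive rate | Power for +27 points |
|---|---|---|
| 25% | 0.021 | 0.79 |
| 27.5% | 0.042 | 0.85 |
| 30% (as planned) | 0.074 | 0.90 |
| 32.5% | 0.121 | 0.94 |
| 35% | 0.183 | 0.97 |

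The planned error rates hold only if the unrepresented patients also have a rate near 30%.

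**4. What restricting the test would cost.** Use the same construction (30% against 57%, exact alpha at most 0.10) with fewer patients:
- n = 18: r = 9, power 0.80;
- n = 12: r = 7, power 0.58.

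**The case against.** Historic controls are always imperfect. PFS is a secondary endpoint in a single-arm feasibility trial, and section 1.1 openly discloses that the series was chemotherapy-eligible. The label can also be read as meaning those members of the series who would meet the trial's criteria, without claiming that every trial group is represented. All of this is fair, and it limits the weight of the point. It does not remove it, because section 9.3 attaches a formal reject rule to a pooled comparison and carries no matching caveat.

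The size of the effect is also open to challenge. The 25-50% ineligibility figure in section 1.1 describes bladder cancer patients in general. It does not describe a trial restricted to ECOG 0-1 cystectomy candidates. The PFS values in the illustration have no source in the documents. That objection stands, so the figures show sensitivity only and are not an estimate.

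A reader might infer three stronger things that the documents do not support:
- **That no medically ineligible Cohort 1 patient of any kind is in the series.** The carboplatin-eligible, PD-L1-positive group could be, and platinum refusers could have counterparts.
- **That the bias favours the experimental treatment.** Its direction cannot be derived.
- **That the historic test must be confined to Cohort 2 and refusers.** This would drop the carboplatin-eligible group without evidence, would assume that all of Cohort 2 matches the series, and would reduce power as shown in step 4 of the working.

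**Conclusion.** The concern holds for one group. The 30% benchmark has no counterpart to Cohort 1 patients medically unfit for any platinum, and nothing in section 9 compensates for this. For the cisplatin-ineligible, PD-L1-positive group the question is open. The sample-size arithmetic is sound; what needs correcting is the description of the reference population and the reach of the conclusion drawn from it.

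The size of the bias cannot be stated. A 5-point error in the pooled reference, in either direction, would be enough to move the false-positive rate to about 0.02 or 0.18. That rests on the assumed mix and on treating the comparison as one with a fixed 30%. The primary feasibility test does not use this benchmark and is unaffected. This is a worthwhile and inexpensive correction to a secondary analysis.

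**What to change.** In sections 9.2 and 9.3:
1. Describe the benchmark as chemotherapy-eligible cystectomy patients who either had no downstaging chemotherapy or did not respond to it. State that the historic comparison supports no PFS conclusion for patients medically unfit for any platinum.
2. Keep the pooled log-rank test. Add Kaplan-Meier 2-year PFS with confidence intervals by cohort, and within Cohort 1 by reason for ineligibility.
3. Fix the classification rule in advance. The Appendix A checklist lets several reasons be ticked, so count anyone with a medical contraindication to all platinum as medically ineligible, even if refusal is also ticked.
4. Add a sensitivity comparison with the historic series that leaves out patients medically unfit for any platinum.

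The cost is SAP wording and a few extra output rows. Cohort and reason for ineligibility are already on the checklist, and enrolment and treatment do not change. The subgroups will be small and imprecise, the sensitivity comparison will have less power than the main one, and the efficacy conclusion will be narrower.
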